7.3 Safety Analysis Set

The Safety Analysis Set (SAS) includes all enrolled subjects who received at least one dose of investigational product in study 20130255. Analyses for safety endpoints and

summary of IP administration will utilize this analysis set. The SAS and FAS are the same analysis sets.

Treatment group identifiers for non-AE safety data based the duration of AMG 334 70 mg and 140 mg exposure will be as follows (see [Section 6.6](#)):

- **AMG 334 70 mg**
- **AMG 334 140 mg**
- **AMG 334 70 mg / 140 mg**

Treatment group identifiers for AE safety data, based on the occurrence of the event relative to their treatment period, will be as follows:

- **AMG 334 70 mg**
- **AMG 334 140 mg**

7.4 PRO Analysis Set

All subjects participating in the PRO substudy and have at least one monthly score for the MPFID will be included in the PRO analysis set. Treatment group identifiers will be the same as the EAS.

7.5 Pharmacokinetic/Pharmacodynamic Analyses Set

The pharmacokinetic analysis set will include all enrolled subjects in the safety analysis set who have at least one evaluable serum AMG 334 concentration post the first dose of IP. **Treatment group identifiers will be the same as the EAS.**

8. Interim Analysis and Early Stopping Guidelines

On an annual basis or until an administrative decision is made to close the study, descriptive statistics of safety and efficacy will be produced for use in the annual report and/or to support publications, if warranted.

An additional interim analysis may be performed for the purpose of inclusion in a regulatory submission to provide additional long-term safety data. This analysis may take place 4-6 months prior to the planned regulatory submission date (2Q 2017) and will include all safety data collected up to 01 September, 2016. There are no stopping rules applied based on any interim analysis and the outcome of this potential interim analysis will not lead to any changes in the conduct of the study.

Safety monitoring will occur in an ongoing fashion by the safety group.

The following summaries will be included for the interim analysis:

- Disposition, demographic, baseline characteristic and baseline disease characteristics, not including efficacy specific data, medical and surgical history, and important protocol deviations
- Adverse events
- Laboratory, vital signs, ECG, liver, antibody and C-SSRS
- Manufacturing lot numbers

9. Data Screening and Acceptance

9.1 General Principles

The objective of the data screening is to assess the quantity, quality, and statistical characteristics of the data relative to the requirements of the planned analyses.

9.2 Data Handling and Electronic Transfer of Data

The Amgen Global Study Operations-Data Management (GSO-DM) department will provide all data to be used in the planned analyses. This study will use the RAVE database. The database will be subject to edit checks outlined in the Data Management Plan (DMP). The eDiary, BSM and ECG data are outside of the RAVE database. All the datasets to be used for planned analyses will be received from **Amgen's Global Study Operations-Data Management (GSO-DM) department**. Additional details will be provided in the DMP and Data Transfer Plan (DTP).

9.3 Handling of Missing and Incomplete Data

Subjects may miss specific data points for a variety of causes. In general, data could be missing due to a subject's early withdrawal from study, a missed visit, or inability to evaluate an endpoint at a particular point in time. For this study, most of the efficacy endpoint will be collected via eDiary and subjects could miss entering several days of data **in between exposures to IP**. The general procedures outlined below describe what will be done when a data point is missing.

Missing eDiary data in the calculation of monthly measurements about subjects' migraine and non-migraine headaches will be handled **using method below**. Unless otherwise specified, all the final analysis and sensitivity analysis will use monthly measurements calculated as follows:

1. **For monthly intervals with ≥ 14 days of eDiary days (days subjects use eDiary and including retrospective eDiary days) in each interval:**
 - a) Monthly frequency measurements (including migraine days, headache days, migraine attacks, cumulative hours of migraine headaches, cumulative hours of migraine headaches with severe pain, acute medication use, etc.) will be

prorated to 28-day equivalents. **Prorated result does not need to be rounded.**

- b) Monthly average severity of migraine pain, migraine related symptoms, **physical impairment scores and impact on everyday activities scores as measured by MPFID** and monthly average scale of migraine interference with daily activity will be calculated as the average of observed scores.
2. **For monthly intervals with < 14 days of eDiary use (including retrospective eDiary days)**, all monthly measurement will be set as missing and will be handled as described in [Section 9.3.2](#)

An information day is a calendar day which is either an eDiary day or headache day and will be used toward headache day proration. The eDiary days will be used toward migraine day proration and medication use day proration.

Missing PROs (MSQ, MIDAS) collected at office visit at certain assessment will not be imputed.

Missing safety endpoints will not be imputed. **Missing day portion of AE start time will be imputed based on [Section 9.3.1](#).**

Missing pharmacokinetic and antibody data will not be imputed.

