4.1 Study Endpoints

Primary Endpoint

The primary endpoint for the study is subject incidence of adverse events.

Secondary Endpoints

- change from baseline in monthly migraine days at assessment time points
- achievement of at least a 50% reduction from baseline in monthly migraine days at assessment time points
- **change from baseline in monthly acute migraine-specific medication treatment days at assessment time points**
- **change from baseline in cumulative monthly headache hours at assessment time points**

Exploratory Endpoints

Change from baseline in

- monthly migraine attacks at assessment time points
- monthly headache (migraine and non-migraine headache) days at assessment time points
- monthly moderate and severe headache (migraine and non-migraine headache) days at assessment time points
- monthly average severity of migraine pain at assessment time points
- monthly average severity of migraine related symptoms (nausea, vomiting, phonophobia, photophobia) for qualified migraine headaches at assessment time points
- migraine-specific quality of life, as measured by the MSQ, version 2.1 at assessment time points
- migraine-related disability, as measured by the MIDAS at assessment time points
- pain interference with daily activities and migraine-specific impact, as measured by the PROMIS Pain Interference Scale short form and single pain and migraine symptom interference questions at assessment time points
- **change in physical impairment over time as measured by the MPFID**
- **change in impact on everyday activities over time as measured by the MPFID**
- AMG 334 pharmacokinetic (PK) concentration
- monthly acute medication use at assessment time points

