4.2 Planned Covariates

There are no planned covariate analyses.

Region (North America vs. Other) and medication overuse (Yes vs. No) as collected on the eCRF in the parent study 20120295, if available, and if not available as collected per the parent study randomization stratification factors may be used for subgroup analysis of the appropriate endpoints.

5. Hypotheses and/or Estimations

This is a single-arm estimation study. No hypotheses will be tested.

6. Definitions

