6.1.2 Efficacy Endpoints

eDiary Day

Day in which a subject uses the eDiary.

Migraine Day

A migraine day is any calendar day in which the subject experiences a qualified migraine headache. A qualified migraine headache is defined either as a migraine with or without aura as outlined below:

1. A migraine without aura is defined as a headache lasting continuously for ≥ 4 hours, and meeting criteria a and/or b:
 - a) ≥ 2 of the following pain features:
 - Unilateral
 - Throbbing
 - Moderate to severe
 - Exacerbated with exercise/physical activity
 - b) ≥ 1 of the associated symptoms:
 - Nausea and/or vomiting
 - Photophobia and phonophobia

OR

2. A migraine with aura and meeting criteria c and d:
 - c) The occurrence of ≥ 1 of the following fully reversible aura symptoms:
 - Visual
 - Sensory
 - Speech and/or language
 - Retinal
 - Brainstem
 - d) Aura is accompanied, or followed within 60 minutes, by headache lasting continuously for ≥ 4 continuous hours (see [Appendix C](#)).

If the subject took a triptan or ergot-derivative during aura or to treat headache on a calendar day, then it will be counted as a migraine day regardless of the duration and pain features or associated symptoms.

Monthly Migraine Days

Monthly migraine days is the number of migraine days **between each monthly IP dose normalized to 28 day equivalents**, relative to study day 1 in the first 3 months, between the month 5 and 6 visit, between the month 9 and 10 visit and **between the month 12 and 13 visit**. Hereafter, the corresponding visits for these intervals will be reported/presented as/referred to month 1, month 2, month 3, month 6, month 10 and

month 13 visit, respectively. All available eDiary data for the visits will be used and prorated to 28-day equivalents.

Qualified Headache

A migraine or non-migraine headache which lasts ≥ 4 continuous hours, or a headache of any duration for which acute medication was administered for treatment of headache.

In particular, a qualified headache is:

- a qualified migraine headache (including an aura-only event that is treated with acute migraine-specific medication), or
- a qualified non-migraine headache, which is a headache that lasts continuously for ≥ 4 hours and is not a qualified migraine headache, or
- a headache of any duration for which acute medication is administered.

Headache Day

Any calendar day in which the subject experiences a qualified migraine or non-migraine headache.

Monthly Headache Days

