Appendix C. Calculation of eDiary Efficacy Endpoints

Calendar-Day-Headache

Every headache (HA) event reported is identified by a unique headache event number.

If a patient responds NO to the question “HA ended while sleeping” in their eDiary then the HA end date-time is defined as the HA end date-time. If a patient responds YES to the question “HA ended while sleeping” in their eDiary then HA end date-time is defined as the wake up date-time.

For each HA whose start and end date-times are not on the same calendar day, so there are one or more midnights (00:00 AM) between the HA start and end date-times, the headache will be split into a consecutive sequence of calendar-day-headaches using the intervening midnights as end and start date-times. For example, if a head starts on May 5 at 08:00 and ends May 7th 13:00 then this headache will be split into 3 consecutive calendar-day-headaches using midnights of May 6th and May 7th, namely from 05May 08:00 to 06May 00:00, 06May 00:00 to 07May 00:00 and 07 May 00:00 to 07May 13:00, respectively.

For the headache whose start and end date-times are on the same calendar day the corresponding calendar-day-headache is that calendar day.

Each calendar-day-headache has a corresponding duration given by:

- calendar-day-headache duration = HA end date-time – HA start date-time.

The calendar-day-headaches will be sorted by headache start date-time in ascending order.

Calendar-Day-Migraine-Headache

A calendar-day-headache is a calendar-day-migraine-headache, if

- it is a migraine without aura, ie, the calendar-day-headache duration is ≥ 4 hours and meet the following criteria a and/or b:
 - a) ≥ 2 of the following pain features:
 - Unilateral
 - Throbbing
 - Moderate to severe
 - Exacerbated with exercise/physical activity

b) ≥ 1 of the associated symptoms:

- Nausea and/or vomiting
- Photophobia and phonophobia

OR

➤ It is a migraine with aura, ie, meet the following criteria c and d:

c) Meeting ≥ 1 of the following fully reversible aura symptoms:

- Visual
- Sensory
- Speech and/or language
- Retinal
- Brainstem

d) Aura is accompanied or followed within 60 minutes by a calendar-day-headache duration ≥ 4 hours.

OR

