- The calendar day is a migraine day (to cover the additional case: the subject took a migraine specific medication (triptan or ergot-derivatives) on that calendar day even without any calendar-day-headache).

Qualified Headache

- a qualified migraine headache (including an aura-only event that is treated with acute migraine-specific medication), or
- a qualified non-migraine headache, which is a headache that lasts continuously for ≥ 4 hours and is not a qualified migraine headache, or
- a headache of any duration for which acute headache treatment is administered

Acute Medication Use Day

An acute medication use day is any calendar day on which a subject uses acute medications. Medications for acute treatment of migraine pain include simple analgesics, combination analgesics, triptans, ergot derivatives and opiates. More specifically, acute medications include triptan-based migraine medications, non-opioid acute headache medications, ergotamine-based migraine medications, opioid-containing acute headache medications, opioid-containing butalbital containing medications and non-opioid butalbital containing medications (medication code is not missing nor equal to “999999”).

Migraine Specific Medication Use Day

A migraine specific medication use day is any calendar day on which a subject uses migraine-specific medication (triptan or ergot-derivatives). Migraine specific medication use day is based on the date-time migraine-specific medication is taken.

eDiary Day

An eDiary day is any calendar day on which a subject has recorded eDiary data. An eDiary day can be identified by the availability of eDiary date-time information for that day such as whether a headache starts and/or ends on that day, the subject woke up on that day while a headache ends during sleep or aura start. An eDiary is also any day on which medication use start date-time is recorded even if no headache is recorded on that day.

Information Day (used for Headache Day calculations)

An information day is any calendar day which is either an eDiary or headache day.

Migraine Attack

A migraine attack is an episode of any qualified migraine headache or episode for which the subject took a triptan or ergot-derivative to treat headache or aura. The following rules will be used for distinguishing an attack of long duration from two attacks, or for distinguishing between attacks and relapses:

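### Monthly migraine days are prorated over eDiary days, but the count is not restricted to eDiary days, so the prorated value can be too high

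*SAP*

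**What the plan says.** **Denominators (SAP Section 9.3).** For headache days: "An information day is a calendar day which is either an eDiary day or headache day and will be used toward headache day proration". For migraine days: "The eDiary days will be used toward migraine day proration and medication use day proration". A month is used if it has at least 14 eDiary days; the rule opens "For monthly intervals with ≥ 14 days of eDiary days (days subjects use eDiary and including retrospective eDiary days) in each interval". SAP Section 6.1.2 adds: "All available eDiary data for the visits will be used and prorated to 28-day equivalents". No cap is stated.

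**Numerator.** SAP Section 6.1.2 defines a migraine day as a calendar day with a qualified migraine headache. It does not require that day to be an eDiary day. Protocol Section 10.1.1.4 also counts days on which a migraine continues. In Appendix C, when a headache crosses midnight, "the headache will be split into a consecutive sequence of calendar-day-headaches using the intervening midnights as end and start date-times". A day is then a migraine day if at least one piece on it qualifies, or if a triptan or ergot-derivative was taken.

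**Link between the two counts.** Appendix C makes every migraine day a headache day. One listed ground for a headache day is "The calendar day is a migraine day (to cover the additional case" of migraine-specific medication taken without a headache).

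**What makes an eDiary day (Appendix C).** Data must be recorded for that day, such as a headache start or end, waking after a headache that ended in sleep, an aura start, or a medication time.

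**Where it is used.** The first secondary endpoint is "change from baseline in monthly migraine days at assessment time points". The 50% responder endpoint is computed from the same monthly value.

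**The concern.** The definition of an information day adds something only if some headache days are not eDiary days, so the SAP expects that to happen. For headache days it puts those days in both numerator and denominator. For migraine days they can enter the numerator while the denominator stays at eDiary days.

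The usual candidate is the middle day of a long headache on which the subject made no entry. Protocol Section 2.1 describes attacks of up to 72 hours, and SAP Section 9.3 expects several days of missed entries in an interval, so the situation is plausible.

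At stake is the accuracy of the monthly value behind the first two secondary endpoints. A reported month could show more migraine days than headache days, or more than 28.

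**Working it through.** **Inputs.** E = eDiary days (at least 14). m = migraine days on eDiary days. k = migraine days that are not eDiary days. H = headache days. I = information days = E plus headache days that are not eDiary days. A 28-day interval is assumed. The SAP prints no proration formula; count × 28 / days is the natural reading.

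**Step 1. The SAP's own example.** Appendix C splits a headache from 5 May 08:00 to 7 May 13:00 into 3 pieces. Splitting at midnight gives 16 h, 24 h and 13 h. That is 3 pieces, as stated, and each is at least 4 h. The start and end times make 5 May and 7 May eDiary days. 6 May is one only if something was entered for it. If the features are met on all three days, this headache supplies 3 migraine days and possibly only 2 eDiary days.

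**Step 2. Formulas.**
- Migraine days as written: 28 × (m + k) / E
- Headache days as written: 28 × H / I
- Migraine days counted on eDiary days only: 28 × m / E

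**Step 3. Illustrations** (no non-migraine headaches, so H = m + k and I = E + k).

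| Case | E | m | k | Migraine days as written | Headache days | Migraine days, eDiary days only |
|---|---|---|---|---|---|---|
| A | 27 | 17 | 1 | 18 × 28/27 = 18.67 | 18 × 28/28 = 18.00 | 17 × 28/27 = 17.63 |
| B | 22 | 14 | 3 | 17 × 28/22 = 21.64 | 17 × 28/25 = 19.04 | 14 × 28/22 = 17.82 |
| C | 14 | 14 | 1 | 15 × 28/14 = 30.0 | 15 × 28/15 = 28.0 | 14 × 28/14 = 28.0 |
| D | 20 | 16 | 8 | 24 × 28/20 = 33.6 | 24 × 28/28 = 24.0 | 16 × 28/20 = 22.4 |

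C and D are extreme. D is eight headaches of the Step 1 pattern plus 4 headache-free diary days.

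**Step 4. When a bound is broken.** The value passes 28 exactly when m + k > E, that is, when off-diary migraine days outnumber migraine-free eDiary days. It passes headache days exactly when (m + k)/E > H/I, which is easier to reach. If k = 0 neither can happen. An enumeration of all 125,868 day-count combinations in 28 days with E of at least 14 found no breach with k = 0.

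The inflation need not show as a breach. If 3 of the 10 migraine-free diary days in case A were non-migraine headache days, headache days would be 21 × 28/28 = 21.0. Migraine days would still be 18.67 rather than 17.63.

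**Step 5. Responder status.** Take baseline 18 (threshold 9), E = 22, m = 6, k = 2. As written: 8 × 28/22 = 10.18, non-responder. eDiary days only: 6 × 28/22 = 7.64, responder. On information days: 8 × 28/24 = 9.33, still a non-responder. The flip depends on the remedy chosen, and the example assumes an unaffected baseline.

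**The case against.** The strongest reply is that a migraine day needs day-level features. Appendix C matches symptoms to calendar-day pieces by headache event number and then by date, using daily symptom records. A skipped day has no such record, so it would not qualify. On that view the two denominators are deliberate: start and end times alone can establish a headache day, while a migraine day needs an entry.

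Much of this stands. A reader might infer that every day a headache spans is counted and that nothing drops an unentered day. The documents do not support that: each piece needs at least 4 h plus features, date matching will remove some days, and retrospective entries will turn others into eDiary days.

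It does not close the gap. The matching rule covers symptoms. Protocol Section 7.2.1.10 lists pain features separately and collects pain severity per headache, and two pain features qualify a piece without any associated symptom. The SAP does not say what happens to a day with no record. If such days were always dropped, some continuation days that Protocol Section 10.1.1.4 counts would be lost without a stated rule.

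Three further points on the other side are right. Medication days are not affected, because a recorded medication time makes the day an eDiary day. Appendix C orders the raw counts only, so migraine days above headache days after proration signal incoherence but break no stated rule. And the consequence is limited: SAP Section 5 says "This is a single-arm estimation study. No hypotheses will be tested", the primary endpoint is adverse-event incidence, and efficacy is descriptive.

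**Conclusion.** The mismatch is real on the SAP as written. Each migraine day that survives symptom matching and is not an eDiary day adds 1 to the numerator and nothing to the denominator. One such day raises the value by 28/E over the eDiary-only value: 28/27 = 1.04 days in case A, and 28/14 = 2.0 days at the minimum diary completeness. Values above headache days, and in extreme cases above 28, are possible.

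This rests on the ratio reading of proration and on pain features being carried by the headache record to an unentered day. The documents do not settle the latter for every feature.

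A reader might infer a known bias in change from baseline or in the responder rate. The documents do not support that. They give no frequency of off-diary migraine days. If these were more common at baseline, improvement would be overstated; if more common on treatment, understated; if similar, the effects could largely cancel.

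**What to change.** In SAP Section 9.3 and Appendix C, state that only migraine days falling on eDiary days, including retrospective ones, are counted, and that they are prorated over eDiary days. Apply the same rule to migraine-headache hours, for which Section 9.3 names no denominator.

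Prorating over information days instead would also keep the value within 28, but it is the weaker choice. It admits an undiaried day only when that day is a headache day, which pulls the estimate up when other days are missing (case B: 19.04 against 17.82). The recommended rule does discard some days known to be migraine days: in case A it gives 17.63, where the count over 28 fully known days is 18.

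Derive parent-study baseline and Month 3 values by the same rule from the existing diary data, at least as a check against the parent-study values. SAP Section 6.3 takes the baseline as defined in the parent study, whose SAP is not among these documents.

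Add a programming check that prorated migraine days never exceed 28 or prorated headache days. Under the recommended rule neither can occur, so a failure would point to a coding error.

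Cost: SAP wording and a small amount of reprogramming, with no new data. Baseline values may differ slightly from those reported in the parent study.
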